## 3. Study Overview

#### 3.1 Study Design

This Phase 4 multicenter, randomized, placebo-controlled, double-blind study is designed to evaluate the efficacy, safety and tolerability of apremilast over 48 weeks of treatment in approximately 285 subjects with early oligoarticular psoriatic arthritis.

Protocol Number: 20200058

Date: 07 February 2023

Page 18 of 67

subjects will be randomized in a 2:1 ratio to either apremilast 30 mg BID or identically appearing placebo via an Interactive Web Response System (IWRS).

Randomization to apremilast arm or placebo arm will be stratified by concomitant use of glucocorticosteroids at baseline (yes/no) and prior/concomitant use of a csDMARD, either MTX or SSZ, (i.e., csDMARD-naïve; csDMARD use prior to baseline [treatment not continued]; or csDMARD use prior to and concomitant at baseline). The number of subjects who are csDMARD-naïve is targeted to comprise up to 50 % of the subjects enrolled in the study. There is no planned protocol extension following the end of the study.

This is a 56-week study which will consist of 4 phases:

- Screening Phase up to 4 weeks
- (Randomized, Double-blind) Placebo-controlled (Treatment) Phase Weeks 0 to 24.
  - Stratified randomization (2:1 ratio to either apremilast 30 mg BID or placebo).
  - Dose-titrated.
  - Subjects with no improvement in SJC (based on sentinel joints, i.e., the joints affected at baseline) at Week 16 are eligible for Early Escape (EE), at the discretion of the Investigator; Placebo-treated subjects who escape early will be transitioned to apremilast 30 mg BID in a blinded fashion via IWRS, while apremilast-treated subjects will remain on the original treatment assigned at baseline.
  - The patients remaining on placebo will be transitioned to apremilast 30 mg BID at Week 24.
  - All subjects who complete this 24-week treatment phase will have the option to enter the Active-treatment Extension Phase.
- (Active-treatment) Extension Phase Week 24 to Week 48.
  - Beginning at Week 24 Visit, all subjects in the Extension Phase will be dispensed open-label apremilast (30 mg BID).
  - All subjects will receive apremilast 30 mg BID until the completion of the study (i.e., up to Week 48 Visit)
- (Post-treatment) Observational Follow-up Phase up to 4 weeks.

[figure not shown]

Protocol Number: 20200058
Date: 07 February 2023
Page 19 of 67

 All subjects who complete the Placebo-controlled Phase or the Extension Phase or discontinue early will participate in the 4-week Observational Follow-up Phase.

 The Observational Follow-up visit should be performed 4 weeks after the last dose of IP.

The study schematic is presented in the following figure:

\*- Subjects with no improvement in SJC (sentinel joints) at Week 16 are eligible for early escape, at the discretion of the Investigator.

Abbreviations: BID = twice daily; csDMARD = conventional synthetic disease-modifying antirheumatic drug; MDA = Minimal Disease Activity; NSAIDs = non-steroidal anti-inflammatory drug.

#### 3.2 Sample Size

Sample size estimation was based on the results from integrated analyses of subpopulation data from five Phase 3 studies (PSA-002, PSA-003, PSA-004, PSA-005, and PSA-006). Assuming a 15% dropout rate by the primary endpoint, a sample size of for the Apremilast 30 mg BID and placebo groups, respectively, will have 80% power to detect a true 15% difference (30% versus 15%) in the proportions of subjects achieving the modified MDA (MDA-Joints) between the Apremilast 30 mg BID and placebo groups, using a chi-square test with a two-sided significance level of 0.05. The calculation was implemented using nQuery 7.0.

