- To evaluate the impact of apremilast 30 mg BID ± NSAIDs and/or csDMARDs vs. Placebo ± NSAIDs and/or csDMARDs on patient reported outcomes (PROs) in subjects with early oligoarticular PsA,
- To evaluate the safety and tolerability of apremilast 30 mg BID ± NSAIDs and/or csDMARDs vs. Placebo ± NSAIDs and/or csDMARDs in subjects with early oligoarticular PsA.

Exploratory Objectives

Study Design

This is a Phase 4, multicenter, randomized, double-blind, placebo-controlled, parallel-group study to evaluate the efficacy, safety and tolerability of apremilast (CC-10004) in subjects with early (≤ 5 years since signs and symptoms began) oligoarticular PsA (according to Classification Criteria for Psoriatic Arthritis [CASPAR] criteria), despite treatment with either NSAIDs and/or ≤ 2 csDMARD. Approximately 285 subjects will be randomized (2:1) to apremilast 30 mg BID or placebo. Treatment assignment will be stratified via an Interactive Web Response System (IWRS) based on concomitant use of glucocorticosteroids at baseline (yes/no) and prior/concomitant use of a csDMARD, either MTX or SSZ, (ie, csDMARD-naïve; csDMARD use prior to baseline [treatment not continued]; or csDMARD use prior to and concomitant at baseline). The number of subjects who are csDMARD-naïve is targeted to comprise up to 50 % of the subjects enrolled in the study. Given that this is a phase 4 study, all subjects are required to meet the existing apremilast regulatory labeling conditions specific to the countries where enrollment will take place (eg, Food and Drug Administration [FDA], European Medicines Agency [EMA], Health Canada). There is no planned protocol extension following the end of the study.

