- Clinical laboratory evaluations

Amgen Inc.

Statistical Methods

Assuming a 15% dropout rate during the Randomized, Placebo-controlled, Double-blind Treatment Phase, a sample size of **approximately** for the active and placebo groups, respectively, will have 80% power to detect a true 15% difference (30% versus 15%) in the proportions of subjects achieving the modified MDA between the treatment groups, using a chi-square test with a two-sided significance level of 0.05. The primary efficacy endpoint, proportion of subjects who achieve the modified MDA at Week 16, between the treatment groups will be compared using a Cochran-Mantel-Haenszel (CMH) test, controlling for concomitant use of glucocorticosteroids at baseline (yes/no) and use of a csDMARD (csDMARD-naïve; csDMARD use prior to baseline; or csDMARD use prior to and concomitant at baseline).

TABLE OF CONTENTS

TITLE P.	AGE	1
PROTOC	COL SUMMARY	4
1.	INTRODUCTION	19
1.1.	Disease Background	19
1.1.1.	Psoriatic Arthritis	19
1.2.	Compound Background	20
1.2.1.	Key Findings from Clinical Studies	21
1.2.1.1.	Efficacy	22
1.2.1.2.	Safety	31
1.3.	Rationale	36
1.3.1.	Study Rationale and Purpose	36
1.3.1.1.	Unmet Medical Need	36
1.3.1.2.	Rationale for the Study Design	36
1.3.1.3.	Rationale for Dose, Schedule, and Regimen Selection	36
1.3.1.4.	Rationale for Choice of Comparator Compounds	37
2.	STUDY OBJECTIVES AND ENDPOINTS	38
3.	OVERALL STUDY DESIGN	44
3.1.	Study Design	44
3.2.	Study Duration for Subjects	47
3.3.	End of Trial	47
4.	STUDY POPULATION	48
4.1.	Number of Subjects	48
4.2.	Inclusion Criteria	48
4.3.	Exclusion Criteria	49
5.	TABLE OF EVENTS	51
6.	PROCEDURES	56
6.1.	Screening Period	56
6.2.	Treatment Period	58
6.2.1.	End of Treatment	58
6.3.	Observational Follow-up	59
6.3.1.	Safety Follow-up	59

Apremilast

Protocol C	C-10004-PSA-013	Amgen Inc.
6.4.	Efficacy Assessments	60
6.4.1.	Modified Minimal Disease Activity–Joints (MDA-Joints) and its Components	60
6.4.1.1.	Joint Assessment	60
6.4.1.2.	Patient's Global Assessments of Disease Activity	60
6.4.1.3.	Patient's Pain Visual Analogue Scale	60
6.4.1.4.	HAQ-DI	61
6.4.1.5.	Enthesitis: Leeds Enthesitis Index	61
6.4.1.6.	BSA	61
6.4.1.7.	Physician's Global Assessments of Disease Activity	61
6.4.2.	Enthesitis:	61
6.4.3.	Dactylitis	62
6.4.4.	Clinical Disease Activity Index for Psoriatic Arthritis (cDAPSA)	62
6.4.5.	Psoriatic Arthritis Disease Activity Score (PASDAS)	62
6.4.6.	High sensitivity C-reactive Protein	62
6.5.	Safety Assessments	63

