9.3. Sample Size and Power Considerations

Sample size estimation was based on the results from integrated analyses of subpopulation data from five Phase 3 studies (PSA-002, PSA-003, PSA-004, PSA-005, and PSA-006). Assuming a 15% dropout rate during the randomized, placebo-controlled, double-blind treatment phase, a sample size of **approximately** for the Apremilast 30 mg BID and placebo groups, respectively, will have 80% power to detect a true 15% difference (30% versus 15%) in the proportions of subjects achieving the modified MDA (MDA-Joints) between the Apremilast 30 mg BID and placebo groups, using a chi-square test with a two-sided significance level of 0.05.

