9.6.3. Primary Efficacy Endpoint

The primary efficacy endpoint, proportion of subjects who achieve the modified MDA (MDA-Joints) at Week 16, between the Apremilast 30 mg BID and placebo groups will be compared using a Cochran-Mantel-Haenszel test, controlling for concomitant use of glucocorticosteroids at baseline (yes/no) and use of a csDMARD: (csDMARD-naïve; csDMARD use prior to baseline; or csDMARD use prior to and concomitant at baseline).

Subjects who have discontinued prior to Week 16 due to lack of efficacy or adverse event will be treated as non-responders in the analysis; and the multiple imputation methodology will be utilized to impute the data for subjects whose modified MDA at Week 16 is missing for a reason other than lack of efficacy or adverse event. Sensitivity analyses will be performed using the non-responder imputation for subjects who have discontinued prior to Week 16, or do not have sufficient information for a definitive determination of the modified MDA (MDA-Joints) status at Week 16.

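### The stated 80% power after 15% dropout is not what the named chi-square test gives with about 285 subjects at 2:1: it is about 74% with dropouts excluded, and 80% survives only to about 2% dropout

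*SAP*

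**What the plan says.** SAP 3.2 states that the sample size "will have 80% power to detect a true 15% difference (30% versus 15" per cent) with a chi-square test at two-sided 0.05. Protocol 9.3 and the Statistical Methods part of the protocol synopsis make the same claim. The synopsis gives the size and ratio: "Approximately 285 subjects will be randomized (2:1) to apremilast 30 mg BID or placebo". SAP 3.1 also gives about 285 subjects and says that "subjects will be randomized in a 2:1 ratio to either apremilast 30 mg BID or identically appearing placebo". The arm sizes in the power sentence are redacted, which is not a fault of the plan.

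The dropout assumption is worded in two ways:
- Protocol 9.3: "Assuming a 15% dropout rate during the randomized, placebo-controlled, double-blind treatment phase". The synopsis says the same. This phase runs to Week 24.
- SAP 3.2: "Assuming a 15% dropout rate by the primary endpoint". The primary endpoint is at Week 16.

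On method, SAP 3.2 adds only that "The calculation was implemented using nQuery 7.0". It names neither the variance formula nor the allocation entered.

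For the primary analysis, Protocol 9.6.3 says that subjects who stop before Week 16 for lack of efficacy or an adverse event "will be treated as non-responders in the analysis; and the multiple imputation methodology will be utilized" for data missing for other reasons. SAP 9.5.1 follows this.

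**The concern.** A power statement that names a test, two rates, an alpha, a dropout rate, a total and a ratio should be reproducible from those inputs. This one is not: the stated inputs give a figure about six percentage points lower.

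If 30% and 15% are rates among completers, the planned risk of missing a true 15-point difference is about 26% to 28%, not 20%. SAP 9.1.3 tests the secondary endpoints in sequence after the primary, so a missed primary test closes the whole hierarchy. Anyone interpreting a null result needs the right planning figure. Type I error, the effect estimate and its confidence interval are not affected.

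**Working it through.** **Inputs.** p₁ = 0.30, p₂ = 0.15, two-sided alpha 0.05 (z = 1.96), chi-square test, 15% dropout (SAP 3.2, Protocol 9.3). Total about 285 at 2:1 (protocol synopsis, SAP 3.1), hence 190 apremilast and 95 placebo. All figures are for the unstratified chi-square test named in the power statement. The power of the stratified Cochran-Mantel-Haenszel test used in the analysis cannot be derived from the documents.

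**Formula.** Power = Φ[(p₁ − p₂ − 1.96·s₀)/s₁], where
- s₀ = √[p̄(1 − p̄)(1/n₁ + 1/n₂)], the pooled null standard error that the chi-square test uses;
- s₁ = √[p₁(1 − p₁)/n₁ + p₂(1 − p₂)/n₂];
- p̄ = (2 × 0.30 + 0.15)/3 = 0.25 at 2:1.

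**No dropout (190/95).** s₀ = 0.05441, s₁ = 0.04947. (0.15 − 1.96 × 0.05441)/0.04947 = 0.876, so power = 81.0%. Exact enumeration of the Pearson test gives 81.7%.

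**15% lost.** 285 × 0.85 = 242, about 161/81. s₀ = 0.0590, s₁ = 0.0537. The argument is 0.64, so power = 73.9% (exact 74.5%).

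**By dropout rate, from 285 at 2:1, dropouts excluded.**

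| Dropout | Power |
|---|---|
| 0% | 81.0% |
| 2.3% | 80.0% |
| 5% | 78.8% |
| 10% | 76.4% |
| 15% | 73.9% |

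The smallest whole 2:1 sample with 80% power is 186 + 93 = 279 evaluable. Exact enumeration is slightly kinder: 184 + 92 (3.2% dropout) still gives 80.2%.

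**Rounding of the total.** Reading *about 285* as 276 to 294 gives 72.4% to 75.3% after 15% dropout, so rounding does not close the gap.

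**Dropouts handled closer to the primary analysis, with 30% and 15% as completer rates.**
- All dropouts as non-responders: 0.85 × 30% = 25.5% against 0.85 × 15% = 12.75% on 190/95. Power = 71.7% (exact 72.9%).
- A mix, assuming that multiply imputed subjects add no information: with 25%, 50% or 75% of dropouts as non-responders, power = 73.3%, 72.7% or 72.2%.

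**Rates already net of dropout.** All 285 count at 30% and 15%: 81.0%.

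**Routes that do return the plan's figures.**
- Unpooled variance at 2:1 (s₁ replaces s₀): 0.15/0.05366 − 1.96 = 0.835, so power = 79.8% at 242.
- Pooled formula at 1:1: 121 per arm gives 80.2% (120 per arm gives 79.8%). 2 × 121 = 242, and 242/0.85 = 284.7, which rounds up to 285.

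**The case against.** The strongest reply is that 80% is reproduced at the stated ratio by a common formula. Unpooled variance gives 79.8%, and the gap may be no more than an option chosen in nQuery. That may well be the origin of the figure. It does not change the power of the test the plan names: exact enumeration puts the Pearson test at 74.5% at 161/81. Even the unpooled Wald test reaches only 78.7% by enumeration, with a type I error of about 5.4% to 5.5%.

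Second, excluding dropouts is a sample-size convention, not the primary analysis. This is true. In addition, SAP 5.4 maps Early Termination values to the next scheduled visit, so some subjects who leave shortly before Week 16 will have a Week 16 value, and 15% dropout need not mean 15% missing. Imputation may also draw on earlier visits. The 72% to 74% range is therefore somewhat pessimistic, by an amount that the documents do not allow one to calculate.

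Third, the rates come from integrated data of five Phase 3 studies, and the binary ACR results that the protocol shows for those studies use non-responder imputation. If the MDA-Joints rates were handled in the same way, they are already net of dropout and power is about 81%. This cannot be excluded. But the 15% allowance would then play no part in the calculation, and the sentence would still need rewording.

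Fourth, the different dropout periods probably follow from Amendment 4, which moved the primary endpoint to Week 16. That explains the mismatch but does not remove it.

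**Conclusion.** The concern holds. With the stated test, rates, alpha, total and ratio, power after 15% dropout is about 74% with dropouts excluded and about 72% if all are non-responders, against 80% stated. By the formula, 80% needs dropout of no more than about 2% (about 3% by exact enumeration). The shortfall of about 6 to 8 points rests on reading 30% and 15% as completer rates. If they are net of dropout, planned power is about 81% and the dropout clause is redundant. The arithmetic is secure; which reading the sponsor intended is not stated. Whether 285 came from an unpooled formula or from a 1:1 calculation cannot be settled from the documents. This should be corrected, but it is a matter of stated planning power and does not touch the validity of the analysis.

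**What to change.** In SAP 3.2, Protocol 9.3 and the synopsis:

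1. State whether 30% and 15% are completer rates or already net of dropout.
2. If they are completer rates, restate along these lines: *About 285 subjects randomized 2:1 give about 81% power with no dropout and about 74% with 15% dropout by Week 16 (chi-square test, dropouts excluded; about 72% if all dropouts are non-responders).* If they are net of dropout, say so and give about 81%.
3. Give the variance formula and the allocation entered in nQuery.
4. Use one dropout period in both documents.

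The cost is wording in three places, and the stated power may look less favourable. The test, alpha, testing hierarchy and enrolment stay as they are; no extra subjects are requested.

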#### 3.3 Adaptive Design

Not Applicable.

Protocol Number: 20200058

Date: 07 February 2023

Page 20 of 67

### 4. Covariates and Subgroups

#### 4.1 Planned Covariates

Covariates includes but not be limited to baseline value for each measured endpoint.

# 4.2 Subgroups

To determine whether the treatment effect is consistent across various subgroups, the primary analysis of the primary endpoint will be repeated for each category, as appropriate, of the following classification variables:

## Subgroups

- Sex (male, female)
- Race (White, non-White)
- Age (< 65, ≥ 65 years)
- Baseline weight (< 70, ≥ 70 to < 85, ≥ 85 to < 100, ≥ 100 kg)

- Region (North America, Europe, Rest of the World [including Russia])
- Baseline glucocorticosteroid use (yes, no)
- Prior/concomitant use of csDMARD, either MTX or SSZ, (naïve, prior use only, prior and concomitant use)
- Prior use of csDMARD (yes, no)
- Concomitant use of csDMARD (yes, no).

The subgroup categories proposed above for the individual demographic and baseline parameters may be adjusted as appropriate. Additionally, the MDA-Joints response rates at Week 16 will be described graphically with forest plots by subgroup.

#### 5. Definitions

# 5.1 Derivations of Efficacy/ Health-related Quality of Life Endpoints

Baseline definition for all efficacy endpoints is given in Section 5.3. Change from baseline is calculated as on-treatment value minus the baseline value. Handling of time points is described in Section 5.4.

#### 5.1.1 Modified Minimal Disease Activity–Joints (MDA-Joints)

For this study, the MDA-Joints (Appendix C of Protocol) is the primary endpoint and is defined as Tender Joint Counts (TJC)  $\leq$  1 and Swollen Joint Counts (SJC)  $\leq$  1 plus 3 of

Protocol Number: 20200058

Date: 07 February 2023

Page 21 of 67

the following 5 criteria: 1) psoriasis Body Surface Area (BSA)  $\leq$  3%, 2) patient pain VAS on a 100-mm scale  $\leq$  15, 3) patient's global assessment on a 100-mm scale  $\leq$  20, 4) physical function [HAQ-DI]  $\leq$  0.5, and 5) enthesitis count  $\leq$  1 based on the Leeds Enthesitis Index. Joint assessment will be based on 66 swollen joints and 68 tender joints. Assessment of tenderness and swelling of the individual joints will be performed by the evaluator; however, calculation of the MDA-Joints will be done programmatically.

Data resource: each component is entered by the physician or the subject via tablets provided by eResearchTechnology, Inc (ERT). The binary value of meeting MDA-Joints criteria or not is calculated in the analysis dataset.

#### 5.1.2 Joint Assessment

TJC or SJC will be derived from the joint assessments entered by the physician via tablets provided by ERT. Joint assessment for tenderness and swelling will be performed for 68 and 66 joints (Appendix D of Protocol), respectively, at every visit. Joint tenderness and swelling will be noted in the following categories, with no quantitation of severity, as shown on the tablet.

- Pain/Tenderness Only
- Swelling Only
- Pain/Tenderness and Swelling
- Permanently Not Assessable
- Temporarily Not Assessable Due to IA Injection
- Temporarily Not Assessable Other

In the event that a joint is injected with intra-articular (IA) glucocorticoid (allowed only after week 24 assessments are completed, and up to the Week 48 Visit), this joint should be marked as "Temporarily Not Assessable Due to IA Injection" if the study visit occurs within 4 weeks (28 days) of the IA injection. In order to maintain consistency throughout the study, the same evaluator should perform the joint assessments for a given subject at a study site at each study visit.

As a joint assessment may be recorded as "temporarily not assessable" or "permanently not assessable", the following data handling rules will be applied to handle the data in the calculation of SJC and TJC.

 Joints temporarily or permanently not assessable at baseline are excluded from joint count throughout the study.

Protocol Number: 20200058
Date: 07 February 2023
Page 22 of 67

 For other un-assessed joints at baseline, the joint assessment at the screening visit, if assessed, is used as the baseline assessment; otherwise, the joint is excluded from joint count throughout the study.

For joints that become either temporarily or permanently not assessable at a
post-baseline visit, the last observed joint assessment (including baseline and
post-baseline assessments) will be used for that visit.

After applying these data handling rules, TJC will be calculated by adding the number of joints with outcomes of 'Pain/Tenderness Only' or 'Pain/Tenderness and Swelling'. SJC will be calculated by adding the number of joints with outcomes of 'Swelling Only' or 'Pain/Tenderness and Swelling'. TJC and SJC will be derived based on the sentinel joints and all joints (66 joints for swelling and 68 joints for tenderness).

#### 5.1.3 Patient's Global Assessments of Disease Activity

The Patient's (Subject's) Global Assessments of Disease Activity (Appendix E of Protocol) is an assessment of how active a subject's psoriatic arthritis was on average during the last week. The subject will be asked to place a vertical line on a visual analogue scale (VAS) on which the left-hand boundary represents the lowest level of disease activity and the right-hand boundary represents the highest. Distance from the mark to the left-hand boundary will be recorded in millimeters, except when calculating cDAPSA score, where the distance will be calculated in centimeters.

Data resource: This VAS is entered by the patient via tablets provided by ERT.

# 5.1.4 Patient's Pain Visual Analogue Scale

The pain in visual analogue scale (VAS) (Appendix E of Protocol) is the subject's assessment of how much pain he/she had, on average, last week in his/her joints due to PsA. The subject will be asked to place a vertical line on a VAS on which the left-hand boundary represents "no pain" and the right-hand boundary represents "pain as severe as can be imagined". The distance from the mark to the left-hand boundary will be recorded in millimeters, except when calculating cDAPSA score, where the distance will be calculated in centimeters.

# 5.1.5 Data resource: Pain VAS is entered by the patient via tablets provided by ERT. HAQ-DI

The HAQ-DI (Appendix F of Protocol) is a 20-question, self-administered instrument that measures the subject's functional ability on a 4-level difficulty scale (0 to 3, with 0

Protocol Number: 20200058

Date: 07 February 2023 Page 23 of 67

representing normal or no difficulty; and 3 representing an inability to perform). Eight categories of functioning are included: dressing, rising, eating, walking, hygiene, reach, grip, and usual activities. This scale is sensitive to change and is a good predictor of future disability. The HAQ-DI score will be set to missing if a subject does not have values for at least 6 of the 8 categories.

Computing the HAQ-DI Score will follow the 2 steps below:

- 1. Find the highest score for each category. If use of aids/devices and/or help from another person are indicated, adjust the highest score for the associated category by increasing a lower score, which is between 0 and 2, to represent underlying disability more accurately. For example, if use of aids/devices and/or help from another person are indicated, adjust the highest score to 2 if the highest score is a 0 or a 1. If the highest score is 2 or 3, retain the value.
- 2. Sum the highest scores from all categories answered and divide it by the number of categories answered (must be a minimum of 6) to obtain an HAQ-DI score of 0-3 (3=worst functioning).

Please note, only one score will be calculated per HAQ-DI assessment.

If the "other" category is checked on the HAQ-DI assessment, then this is expected to be an aide not associated for any of the existing categories, thus this will be excluded from the HAQ-DI score calculation.

Data resource: HAQ-DI is entered by the patient via tablets provided by ERT.

